Data Collection Procedures	
The following data concerning patient treatment and clinical condition will be collected at the indicated time points.
 
Screening Log
 
 
• Ozurdex injected to treat visual impairment due to DME
 
• Number of Ozurdex implant injection in each eye
 
• Patient's age at first Ozurdex implant injection
 
• Date (MM YYYY) of first Ozurdex implant injection
 
• Date (MM YYYY) of last follow-up visit
 
• Anti-VEGF injections before first Ozurdex implant injection
 
• Patient received Ozurdex implants as part or during a clinical study
 
• Reason why the patient has not been selected for the study, if applicable
 
 
Case Report Form
 
Relevant data will be collected at baseline, defined as the period prior to first Ozurdex implant injection (index event), and during the study period, defined as the period between the first Ozurdex implant injection and 1 September 2018.
 
 
• Demographics at baseline (age and gender)
 
• Medical and Ophthalmic history (chronic medical conditions and medical conditions ongoing at time of first Ozurdex implant injections, glaucoma, cataract, and lens status)
 
• Prior and concomitant treatments in the study eye (prior and concomitant cataract and glaucoma procedures, prior and concomitant laser therapy, prior and concomitant intravitreal injections other than Ozurdex [including but not limited to anti-VEGF injections], concomitant medications)
 
• Clinical examinations in the study eye (intraocular pressure measurement, biomicroscopic and ophthalmomicroscopic exams performed)
 
• Contralateral eye information (DME status, treatments for DME received prior and during the study period)
 
• BCVA in both eyes at baseline and during the study period
 
• CRT measured in the study eye at baseline and during the study period
 
• Ozurdex implant injections in the study eye during the study period (date of injections and, if available, reason for initial injection and for reinjections)
 
• AESIs: glaucoma, intraocular hypertension, hypotony, cataract or lens
 

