Ozurdex efficacy in patients with visual impairment due to DME was assessed in 2 randomized, multi-center, masked, sham-controlled, phase III trials, the MEADs trials, over a 3-year period. At study end, 22.2% of patients who received Ozurdex (N=351) had a ≥15-letter improvement compared to 12.0% in the sham group (N=350) ( $p<0.001$ ). Mean BCVA average change over the 3-year period was higher in patients treated with Ozurdex (3.5 letters) than in the sham group (2.0 letters) ( $p=0.023$ ). Mean average reduction in CRT from baseline was greater with Ozurdex 0.7 mg (-111.6  $\mu$ m) than with sham (-41.9  $\mu$ m). In a prospective, multi-center, open-label, 1-year follow-up study, the CHAMPLAIN trial, 27 treatment-naïve patients with type-2 diabetes and affected by DME were treated with Ozurdex. During the one-year follow-up period, most patients (66%) received a second Ozurdex injection with a mean time between injections of  $6.7\pm2.3$  months. One month after the first injection BCVA significantly improved compared to baseline (-0.02 LogMAR) and CRT significantly decreased (-79  $\mu$ m).

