#### 8.2.1 Inclusion Criteria

A patient must meet **all** of the following criteria to be eligible for participation in the study.

1. Patient received at least two Ozurdex implants in the study eye to treat visual impairment due to DME
2. Male or female patient aged  $\geq 18$  years at time of first Ozurdex implant injection
3. First Ozurdex implant injection occurred after 1 January 2015
4. Patient was followed-up at the site for at least 12 months after the first Ozurdex implant in the study eye

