## 10.1 Data Collected in the Screening Log

Once a site has been initiated, site personnel will be invited to complete a screening log with all patients who received at least one Ozurdex implant injection. [REDACTED]

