### **14.2.2.2 Primary Objective**

Number of patients with at least one reinjection and number of reinjections per patient during the year following the first Ozurdex implant injection will be summarized descriptively for all patients from the Analysis population. For patients with more than one year of follow-up, number of patients with at least one reinjection and number of reinjections per patient during the follow-up year considered will be described for each year of follow-up (e.g. 2nd year of follow-up, 3rd year of follow-up...). The number and percentage of patients receiving each injection (first, second, etc.) will be presented for each year of follow-up.

Time between Ozurdex implant injections will be summarized overall and for each reinjection, i.e. first reinjection, second reinjection...

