## **6.0 PATIENT POPULATIONS AND SUBGROUPS**

### **6.1 ELIGIBLE SCREENING LOG POPULATION**

All patients from the screening log who meet selection criteria will be considered in the Eligible screening log population.

As a reminder, site personnel will be invited to complete a screening log with all patients who received at least one Ozurdex implant injection to help them identify eligible patients. Based on data recorded in the screening log, a patient will be considered as meeting selection criteria if s/he meets all the criteria below:

- The number of Ozurdex implant injections is  $\geq 2$  in at least one eye.
- Patient's age at first Ozurdex implant injection is  $\geq 18$  years old
- Date of the first Ozurdex implant injection is  $\geq$  January 2015
- Time from the first Ozurdex implant injection to the most recent follow-up visit prior to 01 September 2018 [DV] is  $\geq 365$  days.
- 'Patient received Ozurdex implants as part or during a clinical trial' is equal to 'No'

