### **6.2 ANALYSIS POPULATION**

The Analysis population will consist of all selected patients for whom an eCRF have been completed and who meet selection criteria (See Section 4.0).

All analyses described in this SAP will be performed on the Analysis Population, unless otherwise specified.

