## **15.0 ANALYSES OF THE OBJECTIVES OF THE STUDY**

### **15.1 ANALYSIS OF THE PRIMARY OBJECTIVE**

The primary objective '*To assess reinjection interval of Ozurdex implants in patients with DME in real-world in Germany and Switzerland*' will be assessed by the following outcomes:

- Total number of Ozurdex reinjections in the study eye during follow-up, and considering years after the first Ozurdex injection in the study eye (See definition in Table 21-1).
- Re[injection interval defined in months as: (Date of injection (j+1) – Date of injection j) ÷ (365.25÷12), for j=1,...,n where n is the number of reinjections in the study eye. The result will be rounded to 0.1.

The number of Ozurdex reinjections in the study eye per year will be first summarized using descriptive statistics for the following parameters:

- The total number and percentage of Ozurdex reinjections received during follow-up.
- Number and percentage (with 95% CI) of patients with at least one Ozurdex reinjection during Year 1 (See definition in Table 21-1), and number of reinjections per patient during Year 1, for all patients in the analysis population. Note: the first Ozurdex injection will not be considered here, only reinjections will be counted.
- Number and percentage (with 95% CI) of patients with at least one Ozurdex reinjection and number of reinjections per patient during Year k (k=2, 3), for patients having a complete Year k of follow-up (see definition of 'Complete year' in Section 21.2).
- Number and percentage of patients receiving each Ozurdex reinjection (first, second, third, etc) for each year of follow-up (Year k, k=1 to 3) considering patients having the complete year of follow-up.

The Ozurdex reinjection interval in the study eye will be described using descriptive statistics for the following parameters:

- Re[injection interval (months) considering all eligible reinjections recorded in the EDC. The 95% CI of the mean will also be presented.
- Re[injection interval (months) considering each reinjection separately (i.e. first reinjection, second reinjection, etc). 95% CI of the mean will also be presented.

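### The Year 1 reinjection percentage is computed only in patients already known to be reinjected, so it overstates the rate among all patients given a first implant

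*SAP*

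**What the plan says.** **Entry.** Protocol 8.2.1 and SAP 4.0 set the same first criterion: "Patient received at least two Ozurdex implants in the study eye to treat visual impairment due to DME". SAP 6.2 carries it into the analysis: "The Analysis population will consist of all selected patients for whom an eCRF have been completed and who meet selection criteria".

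**Analysis.** Protocol 14.2.2.2 plans the "Number of patients with at least one reinjection and number of reinjections per patient during the year following the first Ozurdex implant injection", for the whole Analysis population. SAP 15.1 adds a percentage and an interval: "Number and percentage (with 95% CI) of patients with at least one Ozurdex reinjection during Year 1", on the same denominator. SAP 21.1 makes the interval exact (Clopper-Pearson), and SAP Table 21-1 defines Year 1 as Days 2 to 365.

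**Reach.** Protocol 8.2 and SAP 4.0 expect the findings to carry over to DME patients treated with Ozurdex in the two countries. The bias sections (Protocol 7.3, SAP 7.0) cover volunteer sites, selection of charts, missing or heterogeneous data, and confounding. They do not mention that entry depends on having been reinjected.

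**Screening log.** Protocol 10.1 describes "a screening log with all patients who received at least one Ozurdex implant injection". The fields listed in the protocol synopsis include "Number of Ozurdex implant injection in each eye", the DME indication, age, month of first injection, month of last visit and clinical-study use. SAP 6.1 then limits the Eligible screening log population to patients with two or more implants in an eye, and SAP 9.0 describes only that group. SAP 8.0 plans counts of patients in the logs, patients eligible, and reasons for exclusion.

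**The concern.** A patient with two implants has, by definition, one reinjection. Asking what share of such patients were reinjected in Year 1 is a question about timing among the reinjected. It does not show how often a first implant is followed by a second.

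The figure sits under the primary objective, carries a confidence interval, and comes from a study whose results are meant to generalise to Ozurdex-treated DME patients. Protocol 5.1 itself cites a one-year reinjection percentage from a cohort not described as selected on reinjection: "most patients (66%) received a second Ozurdex injection". Readers will naturally set the two side by side, although they have different denominators. Nothing in the planned output warns them, and the interval reflects sampling error only.

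**Working it through.** **Inputs**

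- Entry condition: at least two implants in the study eye (Protocol 8.2.1, SAP 4.0).
- Denominator: all of the Analysis population (SAP 6.2, 15.1), target 150 (SAP 19.0).
- Illustrative Year 1 rate: 66%, from a study of 27 treatment-naive patients followed for one year (Protocol 5.1).
- Proportion ever reinjected: not given in the documents, so assumed over a range.
- First injections from 1 January 2015 to 1 September 2017; data cut 1 September 2018 (Protocol 9.2).

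**The plan's own figure.** The documents state no expected value or precision for this percentage. Their only precision figure for the primary objective concerns the mean interval: 1.96 × SD / √150 gives 0.24, 0.32, 0.40 and 0.48 months for SD 1.5, 2.0, 2.5 and 3.0. These round to the stated 0.2 to 0.5, so that figure reproduces. It has no bearing on the percentage.

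**Formula.** Take all patients with a first implant who meet the other criteria. Let π1 be the proportion reinjected in Year 1 and π2 the proportion reinjected at any time up to the data cut. Anyone reinjected in Year 1 is also reinjected by the cut, so

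planned percentage = π1 / π2, which is at least π1, with equality only if π2 = 1.

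**Results with π1 = 66%**

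| Assumed π2 | Planned percentage | Overstatement (points) | Exact 95% CI at n = 150 |
|---|---|---|---|
| 100% | 66.0% | 0 | 57.8 to 73.5% (99/150) |
| 90% | 0.66/0.90 = 73.3% | 7.3 | 65.5 to 80.2% (110/150) |
| 80% | 0.66/0.80 = 82.5% | 16.5 | 75.6 to 88.4% (124/150) |
| 75% | 0.66/0.75 = 88.0% | 22.0 | 81.7 to 92.7% (132/150) |
| 70% | 0.66/0.70 = 94.3% | 28.3 | 88.9 to 97.2% (141/150) |

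At π2 = 80% the interval already excludes 66%. With π1 = 50% instead, π2 from 90% to 70% gives 55.6% to 71.4%, an overstatement of 5.6 to 21.4 points.

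**Dependence on start date.** From 1 September 2017 to the cut is 365 days, so a patient who started then and has two implants was almost certainly reinjected in Year 1. The percentage for such starters is close to 100% by construction. From 1 January 2015 to the cut is 1,339 days, so an early starter can qualify through a much later reinjection. The pooled percentage therefore moves with the mix of start dates.

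**Counting rule.** SAP 21.2 ends follow-up at the first concomitant anti-VEGF or corticosteroid treatment and does not say whether this truncates the Year 1 count. If it does, the percentage falls, and late starters need not be near 100%. With the same counting rule in π1, the formula and the direction of the overstatement are unchanged.

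**What the log can give.** It lists patients with one implant as well as those with more, so it yields π2. For illustration, 150 patients with two or more implants and 38 with one give 150/188 = 0.80; with 64 the result is 150/214 = 0.70. The visible fields include no second-injection date, so the log cannot give π1.

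**The case against.** The other side has good arguments, and several stand.

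- SAP 15.1 names the denominator, and the two-implant criterion is listed openly. For that population the percentage is correct.
- The primary objective is the reinjection interval, which exists only for patients with two injections. Criterion 1 suits that objective, and the sample size rests on it. The percentage is one of several descriptive items.
- A reader might infer that single-implant patients disappear from the results. They do not: the disposition counts in SAP 8.0 cover them. What is missing is a reinjection proportion.
- A reader might infer that the log supplies a corrected Year 1 rate. The visible text does not support that. Multiplying the log proportion by the eCRF percentage would give an approximation, but only if selected patients resemble eligible ones. The separate quota for anti-VEGF-naive patients (Protocol 9.2) strains that assumption, and log and eCRF records cannot be linked (SAP 9.0).
- A reader might infer that the confidence interval is invalid and should go. It is valid for the conditional proportion and can stay once labelled.
- The log has its own weakness, since sites are only asked to help: "site personnel will be invited to complete a screening log with all patients who received at least one Ozurdex implant injection". Requiring 12 months' follow-up also drops single-implant patients who left early.

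These arguments limit the point to labelling, a stated limitation and one companion figure. They do not remove it. Naming the Analysis population does not tell a reader that its definition guarantees the outcome being counted, and the generalisability statement invites the wider reading.

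**Conclusion.** The point holds as one of interpretation and reporting. The Year 1 percentage is sound for patients with at least two implants. Read as the rate among all patients given a first implant, it is too high unless every one of them is eventually reinjected.

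The direction follows from the entry criterion alone; the size does not. The range of about 7 to 28 points rests on two assumptions: that 66%, from 27 treatment-naive patients, can stand in for the Year 1 rate, and that 90% to 70% are ever reinjected. It is an illustration, and no single value within it should be quoted as the bias.

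A reader might infer that the primary objective itself fails. The documents do not support that, because this point concerns the percentage and not the interval. It is an inexpensive improvement worth making.

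**What to change.** 1. In SAP 15.1, and wherever the result is reported, label the percentage and its CI *among patients with at least two implants*. Protocol 14.2.2.2 plans the same item, so record the clarification in SAP 22.0.
2. In SAP 7.0 and beside the generalisability statement, say that entry is conditional on reinjection and that the percentage depends on the mix of start dates.
3. Add one table from the screening log: the proportion, with Clopper-Pearson CI, with two or more implants in one eye among all adult DME patients with at least one implant, first injection from 1 January 2015 to 1 September 2017, and no clinical-study use. Give it overall and restricted to at least 12 months' follow-up. Name the DME filter explicitly, since the criteria in SAP 6.1 omit it, and apply dates at month level, as the log records them.
4. Footnote the table as *ever reinjected by the data cut*, not a Year 1 rate, and say that it cannot be linked to the eCRF. Report log completeness by site.
5. Check the log's full field list. Part of Protocol 10.1 is blacked out, and SAP 9.0 uses a log field (gender) that the synopsis does not list. The absence of a second-injection date is therefore established only for the visible text.

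The cost is one label, one limitation statement, one table from fields already planned, and a completeness count. The main drawback is reliance on a log that sites may not have completed fully.

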### Relationship between reinjection interval and drug effectiveness

The potential relationship between Ozurdex reinjection interval and BCVA will be assessed by considering, for each Ozurdex injection  $j$  ( $j \geq 1$ ) in the study eye, the time interval between injection  $j$  and injection  $(j+1)$  and BCVA change from the value prior to injection  $(j+1)$  to 7-12 weeks following injection  $(j+1)$ . All injections of the patient will be considered all together for this analysis.

As a first approach, a figure (scatter plot) defined by Ozurdex reinjection interval (in months) on the horizontal axis and BCVA change (in ETDRS letters) on the vertical axis will be plotted. A linear regression line along with the spearman rank coefficient and p-value will be superimposed on the data of the scatter plot.

As a second approach, the median Ozurdex reinjection interval will be calculated considering all reinjection intervals for a patient. BCVA change (in ETDRS letters) will be then summarized using descriptive statistics by reinjection intervals categorized in two classes according to the median ( $\leq$  median;  $>$  median). The 95% CI of the mean BCVA change will be provided in each class. Based on the observed distribution, other categories than the median may be considered to categorize the reinjection interval.

The same analysis will be performed considering, for each Ozurdex injection  $j$  ( $j \geq 2$ ) in the study eye, the time interval between injection  $j$  and injection  $(j+1)$  and BCVA change from the value prior to the first Ozurdex injection in the study eye (=baseline value) to 7-12 weeks following injection  $(j+1)$ .

A similar analysis will be performed to assess the potential relationship between reinjection interval and CRT in the study eye.

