### Follow-up period

The period starting the day after the day of the first Ozurdex injection in the study eye is the follow-up period (= post-baseline period). End of follow-up occurs at the last study visit or first receipt of concomitant treatment with anti-VEGF and/or corticosteroids, whichever comes first.

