#### Time window (in weeks) after each Ozurdex injection in the study eye

For each Ozurdex injection in the study eye, follow-up visits performed at 7-12 weeks (+/- 2 weeks) (Days [35, 98]) after injection will be described. The time window of 7-12 weeks is relative to the date of each Ozurdex injection in the study eye, where Day 1 = date of the injection (there is no Day 0).

For IOP, BCVA and CRT, which are collected at follow-up visits, the date of assessment is the date of the follow-up visit at which they are reported. Therefore, for each Ozurdex injection, these parameters will be described at the date of assessment and 7-12 weeks after injection. If there is more than one assessment within the 7-12 week time window, then the mean value will be used for analysis considering IOP in mmHg, BCVA in approximate ETDRS letters, and CRT in  $\mu\text{m}$ .

For HbA1c, the date of assessment is collected at follow-up visits. However, assessment of HbA1c will be presented only at baseline and last study visit.

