### **21.3.5 Variables Related to BCVA and CRT**

#### BCVA conversion

The method of assessment for BCVA can be reported in the EDC as ETDRS, Snellen (Feet), Snellen (Meters), or Snellen (Decimal). For analysis, all values will be converted into approximate ETDRS letters.

Snellen converted to approximate ETDRS letters =  $85 + [50 * \log(\text{Snellen fraction})]$

BCVA and CRT: Last assessment prior to each Ozurdex injection

For the first Ozurdex injection in the study eye, the last assessment prior to Ozurdex injection (= baseline assessment) is specifically requested in the eCRF. Therefore, the last assessment is directly available.

For subsequent Ozurdex injections in the study eye, the last assessment prior to the  $j^{\text{th}}$  injection ( $j \geq 2$ ) will be identified considering all assessments available between the day after the  $(j-1)^{\text{th}}$  injection to the day of the  $j^{\text{th}}$  injection included (i.e. date of  $(j-1)^{\text{th}}$  injection  $<$  Date of assessment  $\leq$  Date of  $j^{\text{th}}$  injection). The underlying assumption is that assessments performed at a visit at which an Ozurdex injection is performed are considered as performed before the injection.

BCVA and CRT: Change from baseline to 7-12 weeks following injection  $j$

For each injection  $j$  ( $j \geq 2$ ), the change will be calculated as:

Value at 7-12 weeks following injection  $j$  – Last value prior to the first (baseline) Ozurdex injection in the study eye. See Section 21.2 for the definition of the '7-12 weeks' time window and for the rule in case of multiple assessments within the time window.

BCVA and CRT: Change from the assessment prior to injection  $j$  to 7-12 weeks following injection  $j$

For each injection  $j$  ( $j \geq 1$ ), the change will be calculated as:

Value at 7-12 weeks following injection  $j$  – Last value prior to Ozurdex injection  $j$ . See Section 21.2 for the definition of the '7-12 weeks' time window and for the rule in case of multiple assessments within the time window.

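### The pooled mean reinjection interval gets a 95% CI with no method for repeated intervals from one patient, so the CI is too narrow if those intervals are positively correlated

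*SAP*

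**What the plan says.** SAP 15.1 defines one interval for each reinjection in the study eye. It then describes the interval "considering all eligible reinjections recorded in the EDC. The 95% CI of the mean will also be presented", and separately for the first reinjection, the second, and so on. The inclusion criteria (SAP 4.0) require at least two implants and 12 months of follow-up. Data run from January 2015 to 1 September 2018, so follow-up can reach about 44 months and one patient can supply several intervals. SAP 21.2 adds that "End of follow-up occurs at the last study visit or first receipt of concomitant treatment with anti-VEGF and/or corticosteroids, whichever comes first". The SAP does not say whether this rule decides which reinjections are eligible for the pooled mean.

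SAP 15.2.1 relates interval to effectiveness on pooled data: "All injections of the patient will be considered all together for this analysis". On those points, "A linear regression line along with the spearman rank coefficient and p-value will be superimposed on the data of the scatter plot". When intervals are split at the median, "The 95% CI of the mean BCVA change will be provided in each class". The analysis is done for change from each injection's own prior value and repeated for "BCVA change from the value prior to the first Ozurdex injection in the study eye (=baseline value) to 7-12 weeks following injection". CRT is handled in the same way.

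The only rule on intervals for means (SAP 21.1, Confidence intervals) says that they are two-sided at 95%. Table specifications are in a separate document (SAP 4.0), which was not available.

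**The concern.** The ordinary CI of a mean divides the SD by the square root of the number of observations, and this is valid only if the observations are independent. Intervals from one eye may well not be: a patient whose oedema returns early is likely to be reinjected early each time. Pooling then counts partly repeated information as new.

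The three outputs are exposed differently:

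- **Pooled mean interval (15.1).** The CI is too narrow if intervals are positively correlated within patient.
- **Class means of BCVA or CRT change (15.2.1).** The CIs are too narrow only if the outcome change is positively correlated within patient.
- **Spearman p-value (15.2.1).** It is too small only if interval and outcome change are both correlated within patient.

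The last two conditions are most plausible for change from baseline, because every change for a patient subtracts the same "Last value prior to the first (baseline) Ozurdex injection in the study eye" (SAP 21.3.5). They need not arise for change from each injection's own prior value.

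The pooled mean is a main result for the primary objective. Protocol section 6 states that the objectives rest on no hypothesis, so the p-value serves no stated purpose.

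**Working it through.** **The plan's own figure.** Protocol 14.1 and SAP 19.0 use ω = 1.96 × SD / √n with n = 150 patients. For SD 1.5, 2.0, 2.5 and 3.0 months this gives 0.240, 0.320, 0.400 and 0.480, which round to the stated 0.2, 0.3, 0.4 and 0.5. The formula counts each patient once.

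**Closed form.** Let each patient contribute m intervals with intraclass correlation ICC. The variance of the pooled mean is inflated by DE = 1 + (m − 1) × ICC, and the true coverage of the ordinary CI is 2Φ(1.96/√DE) − 1. Neither m nor ICC is in the documents, so both are assumptions.

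| m | ICC | DE | Coverage |
|---|---|---|---|
| 2 | 0.2 | 1.2 | 92.6% |
| 2 | 0.7 | 1.7 | 86.7% |
| 5 | 0.2 | 1.8 | 85.6% |
| 5 | 0.7 | 3.8 | 68.5% |

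**Simulation with unequal counts.** Assumptions: 150 patients with at least one reinjection; follow-up uniform over 12 to 44 months; generating mean interval 6 months; intervals floored at 1 month. The between- and within-patient SDs are 1.5 and 1.8, so ICC = 2.25/(2.25 + 3.24) = 0.41. Because the reach of the end-of-follow-up rule is unclear, three cases are shown: no early end, and an exponential time to concomitant treatment with mean 24 or 12 months. There were 2000 replicates.

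| Case | Intervals (patients) | Printed half-width | True half-width | Coverage, ordinary | Coverage, clustered |
|---|---|---|---|---|---|
| No early end | 681 (150) | 0.173 | 0.313 | 72% | 95% |
| Mean 24 months | 363 (117) | 0.236 | 0.396 | 75% | 94% |
| Mean 12 months | 219 (93) | 0.304 | 0.456 | 82% | 94% |

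Repeat runs gave ordinary coverage of 70–73%, 73–77% and 78–83% in the three cases, and clustered coverage of 92–95%. With SDs 1.05 and 2.1 (ICC 0.20), ordinary coverage is 85%, 88% and 90%, and clustered coverage is 95–96%. At ICC 0 the ordinary CI covers 94–96%, so the fault disappears when the condition fails. All these coverages are measured around the average pooled mean.

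**Change from baseline (15.2.1).** Suppose all visits have equal variance and pairwise correlation ρ. Two changes sharing one baseline have covariance 1 − ρ and variance 2(1 − ρ), so the outcome ICC is 0.5. Simulation assumptions: interval ICC 0.4; an average of 3 or 4.5 intervals per patient; pairs restricted to j ≥ 2 as in the SAP; 4000 replicates.

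| Outcome ICC | Spearman type I error (3 / 4.5 intervals) |
|---|---|
| 0.5 | 9.7% / 11.7% |
| 0.5, with 70% of 7–12 week windows observed | 7.6% / 10.4% |
| 0.2 | 6.8% / 8.7% |

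Class-mean coverage at outcome ICC 0.5 is 88% / 84% with the ordinary CI and 94% / 95% with the clustered one. A patient-level bootstrap of the Spearman coefficient brings an 11.5% error rate (4.5 intervals, outcome ICC 0.5) to 5.0%.

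**Change from each injection's own prior value.** If the prior values are distinct visits, the same model gives outcome ICC 0. Type I error is then 4.6% / 5.3% and class-mean coverage 95% / 95%, so there is no fault.

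**The case against.** **The absolute error is small.** At ICC about 0.4 the missing half-width is 0.14 to 0.16 months, which is 4 to 5 days at 30.4 days per month. At ICC 0.2 it is about 2 days. Every corrected half-width stays within the 0.5 months that the protocol calls satisfactory. All this stands. It limits the consequence, but it does not make the printed interval a 95% interval.

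**Clustering does not give the typical patient's interval.** Patients with short intervals contribute more of them, and unfinished intervals are not counted. In the simulation at ICC about 0.4 the pooled mean averages 5.2 to 5.4 months although the generating mean is 6.0, and the clustered CI covers 6.0 in well under 20% of runs. This also stands. The correction gives honest uncertainty for the pooled mean that the SAP chose, and nothing more.

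**Correlation can be negative.** The post-injection window is wide ("follow-up visits performed at 7-12 weeks (+/- 2 weeks) (Days [35, 98]) after injection will be described"), so a value in it can also be the last value before the next injection. Under the equal-correlation model, adjacent changes from own prior values then correlate at −0.5, and ordinary class-mean CIs could be too wide. A clustered SE is right for either sign.

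**The text is ambiguous or was not seen in places.** The median interval in 15.2.1 could be read as one per patient, the table specifications are separate, and the software section is partly redacted. A method may be stated elsewhere, but it belongs in the SAP.

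**Pooling is not clearly a change from the protocol.** Protocol 14.2.2.2 already plans an overall interval summary. For the relationship analysis, Protocol 14.2.2.3.1 says each reinjection is considered separately, but its Figure 1 pairs three intervals of one patient and so allows pooling. The p-value is clearly new: the protocol plans only coefficients, and SAP 22.0 does not list it.

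**Conclusion.** The concern holds. As written, SAP 15.1 and 15.2.1 treat repeated values from one patient as independent, and the CI of the pooled mean interval is too narrow under positive within-patient correlation. The absence of a method is certain on the text. The size is not, because ICC, intervals per patient, follow-up distribution and rate of concomitant treatment are all assumed. Over those assumptions, coverage of the primary pooled CI runs from about 93% down to 69%, with a practical error of days rather than weeks. In 15.2.1 the fault is mainly in change from baseline, where the Spearman type I error is roughly 7 to 12%.

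Two things are not at fault: the per-reinjection CIs in 15.1, which use one interval per patient, and the planned precision of 0.2 to 0.5 months. This should be fixed before analysis, but it does not threaten the study.

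**What to change.** Keep the pooled point estimate and change only its uncertainty.

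- **SAP 15.1:** state that the 95% CI of the mean over all reinjections uses a patient-clustered robust standard error (t distribution, contributing patients minus 1 degrees of freedom) or a patient-level bootstrap. State also whether the end-of-follow-up rule in 21.2 decides which reinjections are eligible.
- **SAP 15.2.1:** use the same method for the class-mean CIs. Give no p-value for the Spearman coefficient; a patient-level bootstrap CI may be shown instead. Give the coefficient for each reinjection separately as well. Say whether the median is taken over all intervals or within patient.
- **SAP 22.0:** list the pooling of reinjections in the relationship analysis and, if it is kept, the added p-value.

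A mixed model or a mean of patient means is not proposed, because either would change what is estimated.

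The cost is a few sentences and one variance option. Intervals are already derived patient by patient, so the grouping variable exists, and no further patients or data are needed. The drawback is that most intervals will be wider.
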